#### **Aim 4 (Exploratory): Evaluate whether changes in ER and mindfulness mediate improvements.**

The first step to testing mediation is to assess change in the proposed mediators. Aim 1 analyses address this for ER (Hyp 4a). This procedure will be repeated to see if CAMM scores changed over the duration of the intervention using three waves of data (pre/mid/post measurements) (Hyp 4b). Then, mediator frameworks for clinical trials will be used to assess the degree to which changes serve as mechanisms for EASE effects (Hayes, 2014; Barron & Kenny, 1986). Cast in a path-analysis model, mediation hypothesis will be examined using Mplus software package (Muthén & Muthén, 1998–2012). Considering the fact that the sampling distribution of the indirect effect, represented as the product of two path coefficients, is likely to have a non-normal skewed distribution (MacKinnon et al., 2007; MacKinnon et al., 2002), the inference on the indirect effects will be made based on the bootstrap method which is available in Mplus software package. Considering the nature of Aim 4, which is exploratory and the possibility of many paths, we will employ the following strategy to control the experimental-wise Type I error rate. First, outcome measures will initially be aggregated into four multivariate composite domains (i.e., ER, functional impairment, psychiatric symptoms, and problem behaviors) based on internal consistency analyses and previous studies, which will significantly reduce the number of hypothesis tests initially conducted. Then, exploratory analyses will be conducted for individual measures within these composite domains only if the overall multivariate composite demonstrates a significant mediation effect. All mediation analyses will control for confounds as covariates.

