#### Aim 4 (Exploratory - Mediators): Evaluate whether changes in ER and mindfulness mediate improvements.

- ❑ H4a: Decreased ER impairment will predict decreased functional impairment and psychiatric symptoms.
- ❑ H4b: Increased mindfulness will predict decreased ER impairment.

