**Intent to Treat Analyses and Approach to Missing Data.** Automated systems are in place via our online data collection (piloted during our open trial) to minimize occurrence of missing data. Nonetheless, intent-to-treat analyses of treatment effects will include all 80 individuals, regardless of attrition or infidelity to treatments. Both of our analytic approaches allow for missing data. ANOVA mixed models do not require that subjects be

excluded from the analyses because of a single missing data point. Multilevel growth models can also make an efficient estimation by utilizing all the available data, and further, the estimates are valid (i.e., asymptotically unbiased) when missingness occurs at random (MAR) (Little & Schenker, 1995). Even when MAR is not satisfied, the robustness of the results is maximized when all available data are used in the analysis (Schafer, 1997). In order to accommodate the case of missing ‘not at random,’ we plan to conduct a sensitivity analysis to see how much our inferences would be altered using a pattern-mixture model (Hedeker & Gibbons, 2006).

**Controlling Experimental-Wise Type I Error Rates.** The conduct of multiple tests of statistical inference can artificially increase Type I error rates. Several approaches will be used to control the experimental-wise error rate in this trial. First, analyses conducted to test the hypotheses of Aims 1 through 3 will be given priority over exploratory analyses conducted as part of Aim 4. Since these hypotheses about efficacy and durability of the proposed EASE program on ER and functional impairment have confirmatory nature from our prior studies and are the main hypotheses in this clinical trial, we will employ Hochberg’s correction (Hochberg, 1988) to control the experimental-wise error rate by adjusting p-values for multiple hypothesis tests in order to rigorously examine the treatment efficacy and durability. Second, in order to address the hypotheses in Aim 4, outcome measures will initially be aggregated into four multivariate composite domains (i.e., ER, functional impairment, psychiatric symptoms, and problem behaviors) based on internal consistency analyses and previous studies, which will reduce the number of hypothesis tests initially conducted. Then, exploratory analyses will be conducted for individual measures within these composite domains only if the overall multivariate composite demonstrates a significant mediation effect.

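### The Aim 4 strategy reduces the number of mediation tests but does not control the experiment-wise type I error, as the plan says it does

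*Combined protocol and SAP*

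**What the plan says.** Two places describe the same strategy: the paragraph on controlling experiment-wise type I error in section 1.J.a, and the Aim 4 paragraph under Statistical Analyses by Aim. The Aim 4 paragraph gives the purpose: "we will employ the following strategy to control the experimental-wise Type I error rate".

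- **Step 1.** "outcome measures will initially be aggregated into four multivariate composite domains (i.e., ER, functional impairment, psychiatric symptoms, and problem behaviors"). The type I error paragraph says of this step: "which will reduce the number of hypothesis tests initially conducted".
- **Step 2.** "exploratory analyses will be conducted for individual measures within these composite domains only if the overall multivariate composite demonstrates a significant mediation effect".
- **Test.** "the inference on the indirect effects will be made based on the bootstrap method which is available in Mplus software package".

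The hypothesised paths, in section 1H, are "H4a: Decreased ER impairment will predict decreased functional impairment and psychiatric symptoms" and "H4b: Increased mindfulness will predict decreased ER impairment".

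In the type I error paragraph, Hochberg's correction is attached to the hypotheses of Aims 1 to 3, and Aim 4 then receives the composite strategy as a separate, second approach. No alpha, alpha split, adjusted p-value or adjusted interval is given for Aim 4 at either step. Aim 4 is called exploratory throughout and ranks below Aims 1 to 3.

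**The concern.** Controlling the experiment-wise rate means that the chance of any false claim stays below a stated level whichever of the null hypotheses are true. Aggregation lowers the number of tests, and so the rate, but sets no limit on it. The gate protects the individual measures of a domain only while that domain's composite fails. It does nothing across the composites, and nothing among null measures once a domain has opened.

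Aim 4 is meant to show how EASE works. The damaging case is that treatment moves the mediator but the mediator does not drive the outcomes. The plan foresees it: section 1.K.a allows that ER may change without symptoms following, and that mindfulness may improve without ER doing so. In that case each composite-level path has its own chance of a false mediation claim, while a reader of the plan would take all of them to be covered by experiment-wise control. Section 1.M.a looks ahead to a later trial of mediation, so a false signal could be carried forward.

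**Working it through.** **1. Per-test alpha.** None is stated, so it is inferred from the sample-size section, which gives 49 for d = 0.41 and a low end of 4 (largest d = 2.81) at power 0.80. Take the smallest n for which a one-sample (pre-post) t-test with noncentrality d√n has power of at least 0.80. Two-sided 0.05 gives n = 49 and n = 4, both as stated. For d = 0.41, one-sided 0.05 gives 39 and two-sided 0.025 gives 60. Two-sided 0.05 per test is therefore the natural assumption for Aim 4, but it remains an assumption.

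**2. Number of composite-level paths.** H4a names ER to functional impairment and ER to psychiatric symptoms. H4b names mindfulness to ER. That is k = 3. Adding ER to the remaining domain, problem behaviors, gives k = 4.

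**3. Rate when treatment clearly moves the mediator and no mediator-outcome link exists.** Each indirect effect is then falsely significant about 5% of the time. For independent tests the rate is 1 − 0.95^k:

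- k = 3: 1 − 0.8574 = 14.3%
- k = 4: 1 − 0.8145 = 18.5%

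Correlation between the tests lowers it. For k = 4 the rate is 17.4% at correlation 0.3, 15.6% at 0.5, 11.5% at 0.8 and 9.3% at 0.9.

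**4. Dependence on which path is null.** An indirect effect is a product of two paths, so the rate was also simulated. The inputs were the planned n = 80 and the 60 left after the plan's 25% attrition, with all outcomes sharing one mediator. The first three rows use four outcomes, outcome correlation 0 to 0.8, 2,000 trials per setting and a Monte Carlo product interval standing in for the bootstrap. The last row uses joint significance of the two paths, 3 or 4 outcomes, correlation 0 to 0.5 and 6,000 trials per setting.

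| Treatment to mediator | Mediator to outcomes | At least one false claim |
|---|---|---|
| 0.8 or 1.5 SD | none | about 10-19% |
| none | present | about 5-6.5% |
| none | none | 1% or less |
| 0.3 / 0.4 / 0.5 SD | none | about 2-5% / 4-8% / 6-11% |

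The second row stays near 5% because all the tests share the same null first path.

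**5. Individual measures.** If every composite is null, individual measures are tested only after a composite has already given a false positive. That trial is already counted, so the gate adds nothing to the chance of at least one false claim. If a composite is truly mediated, its gate opens properly, and m null measures inside it, each at 0.05 and independent, give 1 − 0.95^m: 9.8% (m = 2), 14.3% (m = 3), 18.5% (m = 4).

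**6. After adjustment.** With four composites and 0.05/4 = 0.0125 each, the composite-stage rate is 1 − 0.9875^4 = 4.9% if independent, and about 4.4% at correlation 0.5.

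**The case against.** The strongest reply is that Aim 4 is exploratory. The plan says so repeatedly, concedes limited power for mediation, gives Aims 1 to 3 priority and Hochberg's correction, and defers a fully powered mediation test to a later trial. An exploratory aim needs no error control. That is right, and it limits severity. It does not justify stating a property that the strategy lacks.

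The second reply concerns size, and much of it stands. The high rates need a clear between-arm effect on the mediator. The pilot EDI Reactivity effect of 0.73 is an uncontrolled pre-post change in 11 participants, whereas the trial compares EASE with a time-matched active control. At 0.3-0.5 SD between arms the rate is roughly 2-11%. But control has to hold under every null configuration, so a low rate in some of them does not rescue the claim.

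A reader might infer that the true rate is 10-30% where the plan promises 5%. The documents do not support that. They state no target rate and no alpha, and the absence of adjustment is read from silence. The 30% end (1 − 0.95^7 = 30.2%) needs seven independent mediator-by-domain paths. The Aim 4 text mentions that many paths are possible, but it lists no such set.

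A reader might also infer that the individual-measure tests always add to the composite-stage error. Step 5 of the working shows that they do not when all composites are null.

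**Conclusion.** The concern holds as a mismatch between the stated property and the procedure: the Aim 4 strategy reduces the number of tests and does not control the experiment-wise rate. At an assumed two-sided 0.05 per test, the composite stage can reach about 14% for three paths and 18.5% for four, in the configuration where treatment clearly moves the mediator but the mediator does not drive the outcomes. It would be higher with more paths, and lower with correlated outcomes or a modest mediator effect. Two to four null measures inside a truly mediated domain bring a further risk of about 10-19% in that domain.

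These figures rest on the assumed alpha, on the absence of any unstated adjustment, and on simulations with a single shared mediator. Severity is minor to moderate. No efficacy conclusion depends on Aim 4, and nothing here affects Aims 1 to 3.

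**What to change.** In both the type I error paragraph and the Aim 4 paragraph, do one of the following.

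1. **Make the claim true.** State the alpha and list the k composite-level indirect effects. Apply Hochberg to their bootstrap p-values, or judge them with bootstrap intervals at level 1 − 0.05/k (98.75% for k = 4). Apply the same kind of adjustment among the measures within any domain that passes. For control over the whole of Aim 4, use the interval version and let each opened domain use only its own share, 0.05/k, for its measures. A fresh 0.05 in each of four opened domains, each containing null measures, could again reach 1 − 0.95^4 = 18.5%.
2. **Drop the claim.** Replace *control* with *reduce*, and state that Aim 4 has no experiment-wise error control and is hypothesis-generating.

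Either is a sentence or two, with no new data. The first option costs somewhat wider intervals, and so some power, in an aim that the plan already regards as underpowered. The second costs no power and fits the exploratory label.

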#### **1.K.a. Potential Challenges, Alternative Strategies, and Design Considerations**

*What if EASE does not work?* Although our preliminary data suggest that EASE will have a positive impact, it is possible that this RCT with a larger sample will not yield consistent results. Even if there is not evidence for the efficacy of EASE, results will inform our understanding, and treatment, of ER-related problems in ASD. It is possible, for instance, that mindfulness improves but not ER in measurable ways. It is also conceivable that ER moves but that this change is not reflected in symptomatic improvement. This study is designed such that, even if unsuccessful, the results will inform subsequent treatment research in this area.

*How will we handle use of other treatments?* EASE takes about 16 weeks to complete from start to finish (plus the 3-month follow-up). Based on our pilot studies and prior clinical work, we anticipate most participants will be involved in other treatments. We will not enroll participants who are actively engaged in treatment that targets ER; however, treatments such as speech therapy and family counseling will be permitted. Pharmacological treatment is permitted as well. Given prior research and the sample in our pilot study, we anticipate the majority of this sample will be medicated, and medication changes (e.g., altered dosages) are common, even though inclusion requires medication to be consistent at enrollment without planned changes. We will collect data on other treatments and changes in medication so that we can subsequently determine if this is associated with response.

*Why a high-functioning sample?* We deliberated on the minimum level of cognitive and verbal ability necessary for participation in this treatment, and have determined that the program is likely to be most accessible to people who do not have co-occurring intellectual disability (ID) and are verbally communicative; as such we have restricted eligibility with regard to verbal ability. Additionally, there are unique risks faced by people without ID during transition to adulthood (Taylor & Mailick, 2014), and emotional problems and high negative affect are most pronounced among higher functioning adolescents with ASD, compared to lower functioning peers (e.g., Sukhodolsky et al., 2008).

*Why a 2-site study rather than single site?* There is a major research to practice gap in our field; indeed, on average there is a lag of about 10 years before interventions that are research-supported are well-disseminated in clinical practice. The conduct of multi-site trials should help decrease the gap, as it requires development of manuals that can be adopted across sites, and therapist training materials. Second, [name] and [name] offer complementary expertise to this study – [name] is an expert on assessment and presentation of ER impairment in ASD, while [name] has expertise in treatment development, RCT design, and clinical evaluation in ASD. Third and finally, the two-site approach will permit ascertainment of a large and diverse (in terms of both ethnicity and SES) sample.

*Why not use ecological momentary assessment (EMA) or other biological measures?* We considered EMA to measure ER in the natural environment; however, difficulties in EMA adherence and time commitment

were seen in [name] & [name]’s open pilot trial MBI with young adults with ASD. Responses to text message alerts concerning current emotion ratings (randomized to 2-3 times a week) in the sample ranged from 0-100% (n=9). We considered neuroimaging, but opted to first emphasize real-world, behavioral and functional outcomes. Finally, while we would like to explore physiological arousal in future studies, it is not an ideal starting point given inconsistencies in the association between physiological measures and stress response in ASD. We have a collaborator in the Dept. of Engineering at the University of Pittsburgh ([name]) who is an expert in EEG and machine learning, and we are currently designing paradigms that would be ideal for pre- and post-EEG in this context. Should this proposal be funded, we hope to utilize additional resources to add EEG to our assessment battery with [name] overseeing data collection and analysis.

### 1.L.a. Timeline

Figure 8. Study Timeline

| Tasks  | Year 1 |  |       | Year 2 |       |       | Year 3 |       |   | Year 4 |   |   |
|--|--------|--|-------|--------|-------|-------|--------|-------|---|--------|---|---|
| DOD regulatory review  | █      |  |       |        |       |       |        |       |   |        |   |   |
| Therapist training (cross-site)                              | █      |  |       |        |       |       |        |       |   |        |   |   |
| Dual site QA checks (data management, supervision, fidelity) | █      |  |       |        |       |       |        |       |   |        |   |   |
| Pitt participant recruitment (n = 50)*                       |        |  | 6 4   | 6 4 4  | 6 4 4 | 6 4 4 | 4 4 4  | 4 4 4 |   |        |   |   |
| VT participant recruitment (n = 30)*                         |        |  | 4 2 2 | 4 2 2  | 4 2 2 | 4 2 2 | 4 2 2  | 4 2 2 |   |        |   |   |
| Screening and randomization                                  |        |  |       | █      | █     | █     | █      | █     | █ | █      | █ | █ |
| Collection of pre-, mid-, post-, and follow-up data          |        |  |       | █      | █     | █     | █      | █     | █ | █      | █ | █ |
| Data analyses  |        |  |       |        |       |       |        |       |   | █      | █ | █ |
| Dissemination (conference presentations & publications)      |        |  |       |        |       |       |        |       |   | █      | █ | █ |

\*Estimated participant recruitment flow, in even numbers for randomization

### 1.M.a. Summary: Significance and Innovation

- Treatments that bridge adolescence through early adulthood are needed to prevent the developmental plateau, and often regression, attributed to the service ‘cliff’ and lack of effective treatments during this developmental period for those without co-occurring intellectual disability. EASE was specifically developed for this population and developmental period, using a participatory action approach to ensure it meets the needs of teens and young adults with ASD (and their parents), and to maximize feasibility and ultimate dissemination.
- Consistent with the current emphasis in treatment development research adopted by the National Institutes of Health, EASE emphasizes engaging an underlying target mechanism, namely ER. By improving emotion awareness and mindfulness, EASE is hypothesized to improve ER directly, which we believe will have downstream effects of a host of behavioral problems including aggression, hostility, and depression, as well as functional independence.
- The modularity and flexibility of EASE permits therapists to make the program highly personalized, which is critical given the tremendous clinical heterogeneity in this population.
- The study design is rigorous, with use of an active control condition, blind raters, and two sites. Inclusion of the active control is much stronger test than the traditional waiting list control. By having two sites, we are able to reach the target sample size and also ensure that EASE can be implemented with fidelity across sites and providers, which is critical for subsequent dissemination. Further, by ensuring equivalence across the sites in all aspects of study implementation (e.g., recruitment, data collection) we will be well-prepared for subsequent evaluation of mediation in a fully powered multi-site trial.
